A randomized controlled trial comparing cosmetic outcomes of pediatric laceration closure using a tissue adhesive (Dermabond™) versus adhesive strips (Steri-Strips™) versus absorbable sutures

Study Protocol

NCT ID: NCT03280628

Document Date: 8/10/2017

Principal Investigator:
[name], MS
Vanderbilt University Medical Center
Pediatric Emergency Medicine
[name]
[name]

Table of Contents		
Section	Topic	Page
I	Specific Aim and Study Hypothesis	3
II	Summary of Approach	3
III	Background	3
IV	Rationale	4
V	Inclusion and Exclusion Criteria	4
VI	Subject Recruitment and Enrollment	4
VII	Study Procedures	5
VIII	Predictor Variables	5
IX	Outcome Variables	6
Χ	Ethical Considerations	7
ΧI	Risks of Study Participation	7
XII	Reporting of Adverse Events or Unanticipated Problems involving Risk to Subjects or Others	7
XIII	Study Withdrawal or Discontinuation	7
XIV	Data Management	8
XV	Statistical Considerations	8
XVI	Privacy and Confidentiality Issues	8
XVII	Follow-up and Record Retention	9
XVIII	Data Safety and Monitoring Plan	9
XIX	References	9

I. Specific Aim and Study Hypothesis

Specific Aim: The specific aim of this study is to determine the best of 3 different methods of closure of simple pediatric lacerations in terms of cosmetic outcome, pain, need for sedation, cost and length of ER stay.

Hypothesis: We hypothesize that the closure of simple pediatric lacerations with either a tissue adhesive (DermabondTM), or adhesive strips (Steri-StripsTM) will provide clinically equivalent cosmetic outcomes to absorbable sutures while reducing pain, need for sedation, cost and length of ER stay without increasing the risk of complications.

II. Summary of Approach

To address the Specific Aim we will conduct a 3-arm randomized controlled trial comparing methods of closure of simple pediatric lacerations. The 3 arms will be: DermabondTM, Steri-StripsTM, and absorbable sutures (our control arm).

We will examine the association between closure method and the primary outcome variable, cosmesis of the resultant scar.

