As a secondary aim we will assess for statistically significant differences in the degree of pain experienced by the patient, in the need for sedation, in the cost of each closure method, and in the length of the patient's ER stay. We anticipate that the treatment arms (DermabondTM, Steri-StripsTM) will demonstrate no clinically significant difference in cosmetic outcomes while reducing the pain experienced by patients during laceration closure, reducing the need for sedation, reducing costs and reducing the length of patients' ER stays.

III. Background

Lacerations are a very common presentation in pediatric Emergency Departments (ED). In fact, over the past 2 years (February 2015-2017), there were a total of 3100 lacerations repaired in the ED at Monroe Carell Jr's Children's Hospital at Vanderbilt (VCH). This can be a painful and traumatic procedure for children, especially young children. Given that most lacerations occur in young children (74.1% in those less than 6 years old), it is important to use noninvasive and painless closure methods when possible. ^{10, 11, 15}

Historically, sutures have been the preferred method of closure for lacerations.¹⁸ While they have been made of different materials over the years, the general concept of needle and string has remained mostly consistent.¹⁸ However, new methods of wound closures have been developed since. Surgical tape was first developed by surgeon Horace Day in 1845.⁵ The earliest versions of surgical tape had several issues including proper adhesion, skin irritation, blocking of perspiration, etc.⁵ The modern version of surgical tape that we are now familiar with (Steri-StripsTM) has been around since the 1960s, and except for a few minor modifications, it has largely gone unchanged.³⁵

Tissue adhesives, derived from cyanoacrylate, were invented in the 1940s and have been used for decades for wound closure outside of the United States.³ However, it wasn't until 1998 that the Food and Drug Administration approved 2-octyl cyanoacrylate (DermabondTM) for use in the United States.³⁶

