- v. Laceration less than 5 cm in length and 0.5 cm in width
- vi. Laceration less than 12 hours old
- vii. Laceration minimally contaminated (no visible dirt in wound)

b. Exclusion criteria

- i. Significant medical history that may impact wound healing (hematologic or oncologic diagnosis requiring chemotherapy, ichthyosis, epidermolysis bullosa, etc.)
- ii. Use of oral steroids (more than 5 days in the past month)
- iii. History of keloid formation
- iv. Allergy to tissue adhesives, adhesive strips, or topical anesthetics
- v. Lacerations requiring deep sutures
- vi. Lacerations caused by animal bites or scratches
- vii. Lacerations located on the scalp, eyebrow, eyelid, lip, mucosa, joint or nail
- viii. No access to photographic capabilities (camera or smartphone) and/or email, or unable to return to the VCH ED to have a picture taken

VI. Subject Recruitment and Enrollment

We will enroll a sample of 90 children and adolescents 0 to <18 years of age. All eligible patients will be recorded in the Screening Log (see Appendix I).

Subject identification and enrollment will be performed by trained study staff stationed in the VCH ED. The study staff enrolling the patient will obtain written informed consent and/or

assent, as applicable (see Consent Form and Assent Forms). Study staff will also complete a

Subject Enrollment Form (see Appendix II) and Subject Data Form (see Appendix III) which will be maintained in a locked file in the ED.

Institution/Hospital: Vanderbilt Children's Hospital

VII. Study Procedures

Study Design

The study design will be a single-blind, randomized controlled trial. After enrollment, all participants will have LET placed and their wound washed out with sterile normal saline.

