Depending on which arm they are randomized to, participants will have their laceration closed by either DermabondTM, Steri-StripsTM, or absorbable sutures per the treatment arm protocols (Protocols, see Appendix IV). Unfortunately, given the nature of the study, neither the patient, parent nor health care provider will be blinded to the method of closure. Additional topical or injected anesthetics or the use of sedation will be left up to the patient/parent and provider's discretion. After the procedure, both patient (if older than 3 years old) and parent/guardian will be asked to fill out a short questionnaire (Questionnaires, see Appendix VI). The parent/guardian will be asked to rate the appearance of 3 images of random scars. All parents/guardians in the study will rate the same 3 scars to establish a baseline for each parent. The health care provider will also be asked to fill out a short questionnaire (Questionnaires, see Appendix VI). Upon discharge, the participant and their parent/guardian will be provided with verbal and written return precautions by the study staff (Care Instructions, see Appendix V).

Parents/guardians will be called 3 months after their initial visit for a brief over-the-phone interview (Questionnaires, see Appendix VI). At this time, they will be prompted to take a picture of the scar and send it to the Investigator by e-mail. A Vanderbilt email address has been set-up and is secure per Vanderbilt criteria. As an alternative, they can come back to the VCH ED where study staff will ask them a couple of questions in person and take a picture of the scar.

Every effort will be made to de-identify the images of the scar (using image editing software to crop everything on the image but the scar with some surrounding skin). The images will then be collected and presented to two Plastic Surgeons who will be blinded to the method of closure. They will subsequently score the scar as seen in the images (Questionnaires, see Appendix VI). All data will be collected on paper and then transferred to REDCap®. Each piece of data will be transferred to REDCap® by two study staff independently and then examined for any differences which can be reconciled by examining the paper forms. This will prevent errors in transferring data from paper to electronic format.

Participants will be compensated with a \$15 check after completion of the 3 month questionnaire and sending of photo.

Randomization

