This secondary outcome will be evaluated by the patient (if age-appropriate), parent and provider at the time of the ER visit (Questionnaires, see Appendix VI). Patients aged 3 to 12 will be asked to rate their pain on a Wong-Baker FACES® Pain Rating Scale (licensing for use in progress). Patients aged 12 to 18 will be asked to rate their pain using a 100 mm Visual Analogue Scale with a score of 0 corresponding to "No pain" and a score of 100 corresponding to "Terrible pain." Parents and providers will each be asked to score how much pain they felt the patient experienced on the same Visual Analogue Scale.

ii. Need for anesthetics/anxiolytics/sedation

This secondary outcome examines the need for adjuncts to control pain/anxiety including LET, injected lidocaine, anxiolytics or systemic pain medications, ketamine sedation or others. Data will be collected by study staff observing the procedure. Data will also be extracted from the patient's Electronic Medical Record.

iii. Length of procedure

This secondary outcome, measured in minutes, will be collected by study staff observing the procedure.

iv. Cost of visit

This data will be extracted from the patient's Electronic Medical Records and from the Billing Department.

v. Length of ER stay

This data will be extracted from the patient's Electronic Medical Records.

vi. Resource utilization

Institution/Hospital: Vanderbilt Children's Hospital

This secondary outcome examines the need for personnel in the room to keep the child calm or still. This data will be collected by study staff observing the procedure.

vii. Likelihood that parent would recommend wound closure type

This secondary outcome will be measured using a 100 mm Visual Analogue Scale with a score of 0 corresponding to "Extremely unlikely" and a score of 100 corresponding to "Extremely likely." This data will be extracted from the parent questionnaire at the time of the ED visit (Questionnaires, see Appendix VI).

viii. Complications

Prevalence of complications (infection, dehiscence, etc.) will be evaluated. This secondary outcome will be obtained during the brief phone questionnaire with parents at 3 months after the ED visit (Questionnaires, see Appendix VI).

ix. Poor cosmetic outcome

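### Does listing LET as an adjunct, when every participant receives it, spoil the secondary outcome on need for anesthetics and sedation?

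*Combined protocol and SAP*

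**What the plan says.** Section VII (Study Procedures, Study Design) sets a common first step before closure: "After enrollment, all participants will have LET placed and their wound washed out with sterile normal saline". This does not depend on the arm. The same section then says: "Additional topical or injected anesthetics or the use of sedation will be left up to" the patient or parent and the provider. So one LET application is fixed by protocol, and anything beyond it is discretionary.

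Section IX.b.ii defines the secondary outcome on anesthetics, anxiolytics and sedation. It "examines the need for adjuncts to control pain/anxiety including LET, injected lidocaine, anxiolytics or systemic pain medications", and the list ends with ketamine sedation and an open category. Study staff who watch the procedure collect the data, and a second source is named: "Data will also be extracted from the patient's Electronic Medical Record". The section does not say whether the items are reported one by one, counted, or merged into a single yes/no variable. Nor does it say whether LET here means the routine application or a further one.

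Section I hypothesizes equivalent cosmetic results "while reducing pain, need for sedation, cost and length of ER stay without increasing the risk of complications". Section II gives the secondary aim as testing for "statistically significant differences in the degree of pain experienced by the patient, in the need for sedation" and in the other secondary measures. Section XV (Statistical Considerations) deals only with the continuous cosmesis score.

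**The concern.** Something given to everyone by protocol cannot measure need. If LET in Section IX.b.ii includes the routine application, that item is the same in every arm.

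The worry grows because no scoring rule is given. An analyst who defined the outcome as use of any listed adjunct would find every participant positive and no possible difference between arms, however much lidocaine or ketamine use differed. Sedation is named in the hypothesis and the secondary aim, yet Section IX gives it no outcome of its own; it appears only in this mixed list. One could therefore fear that a stated hypothesis has no usable variable, or that its summary would be chosen after the data are seen, in a trial where patient, parent and provider all know the closure method. Drawing some data from the medical record adds a doubt about whether routine and additional LET can be told apart.

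**Working it through.** The documents give no adjunct or sedation rate and no power figure for this outcome, so there is no figure of the plan's own to reproduce. The check is what the constant LET item does under each way of scoring the list.

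**Inputs**
- LET use by protocol: L = 1 in every arm (Section VII).
- Planned size: 30 per arm, 90 in total (Section XV).
- Test: Fisher exact, two-sided 0.05, pairwise and without multiplicity adjustment (assumed; the plan names no test for this outcome).
- Rates r of adjunct use beyond routine LET: assumed, for illustration only.

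**1. Item by item.** The LET row is 30/30, 30/30, 30/30. Every other row has its own numerator and does not involve L. For an assumed 40% against 10% on one item, exact power is 0.705 at 30 per arm. It is 0.705 whether or not a LET row stands in the same table. Loss from the overlap: none.

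**2. Count of adjuncts.** Let K be the number of adjuncts beyond routine LET. The score is 1 + K for everyone. Then
- difference in means = (1 + mean K in arm A) − (1 + mean K in arm B) = mean K in A − mean K in B;
- the variance of 1 + K equals the variance of K.

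Loss from the overlap: none.

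**3. Any listed adjunct, routine LET counted.** If LET and the other adjuncts are independent, P(any) = 1 − (1 − L)(1 − r).
- L = 1: P(any) = 1 for every r. The table is 30/30 against 30/30, Fisher p = 1.0, power 0.
- L = 0.95, r = 0.50 against 0.20: 1 − 0.05 × 0.50 = 0.975 against 1 − 0.05 × 0.80 = 0.960. Exact power is below 1%.
- L = 0.90, same r: 1 − 0.10 × 0.50 = 0.95 against 1 − 0.10 × 0.80 = 0.92. Exact power is again below 1%.
- The same r of 0.50 against 0.20 with LET left out: exact power 0.596.

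The loss here is close to total, and imperfect adherence to LET does not rescue the score.

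**4. Any adjunct beyond routine LET.** L drops out, P(any) = r, and the comparison is as informative as 30 per arm allows. For assumed rates the exact power is 0.241 (20% against 5%), 0.372 (30% against 10%), 0.596 (50% against 20%) and 0.851 (60% against 20%). These figures describe the trial's size. They do not measure the overlap.

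**Which scoring do the documents support?** Section IX.b.ii lists distinct kinds of adjunct and mentions no composite. Section VII separates the routine application from what is additional and discretionary, and need fits only the second. Sections I and II single out sedation, and ketamine sedation is a named item. Scorings 1, 2 and 4 are all compatible with this. Scoring 3 is not excluded, but no section asks for it, and its result would be visibly degenerate at the first tabulation.

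**The case for a change.** The strongest case for a change is that the fix is cheap and the text is loose. Section VII draws the right line between routine and additional anesthetic, and Section IX.b.ii then drops the qualifier and writes plain LET. With no scoring rule anywhere, a hypothesis named in Section I depends on a choice made later, by people who may know the allocation. One or two sentences would settle it.

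Much of that stands as description. The overlap is in the text, the qualifier is missing, and so is the scoring rule. What does not stand is the step to harm. The damage needs an any-adjunct composite that counts routine LET, and no section describes one. The lack of an analysis rule for sedation is a general feature of a plan whose statistical section covers only cosmesis; the LET entry does not cause it, and removing LET from the list would not cure it. The doubt about the medical record is conjecture: observation by study staff is the first source named, and the data forms and questionnaires in Appendices III and VI, which would show how LET is coded, are not in the supplied text. A missing field cannot be inferred from that.

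**Conclusion.** No change follows. Under full adherence to Section VII, a yes/no LET item that includes the routine application is constant at 100% across arms and carries no between-arm information; if the item means further LET, it can differ. Either way the other listed adjuncts, sedation included, can be compared at the planned 30 per arm with no loss under per-item, count or beyond-routine scoring. Only a composite that counts routine LET would fail, and it would fail completely (p = 1.0).

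This rests on two assumptions: that the items are recorded separately, which the list suggests but the supplied text does not confirm, and that the analyst reads need in the light of Section VII's own distinction. An analyst who tabulates the items by arm and shows sedation as its own row answers the question in Sections I and II from the data already planned. The omission is missing detail in one of ten secondary outcomes; the primary outcome, the sample size, randomization and safety reporting are not affected.

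### The complications outcome (IX.b.viii) rests on parent report at 3 months alone; the protocol does not bring events in the ED, or changes of closure method before discharge, into a comparison by arm

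*Combined protocol and SAP*

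**What the plan says.** The hypothesis in section I is that the two non-suture methods match sutures cosmetically while "reducing pain, need for sedation, cost and length of ER stay without increasing the risk of complications". Section II repeats the expectation that sedation will be needed less with those methods.

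Complications are the eighth of ten secondary outcomes. Section IX.b.viii reads "Prevalence of complications (infection, dehiscence, etc.) will be evaluated", and gives the source: "This secondary outcome will be obtained during the brief phone questionnaire with parents at 3 months after the ED visit". Section VII (Study Design) adds a substitute for the call: "As an alternative, they can come back to the VCH ED where study staff will ask them a couple of questions in person". This takes place at the same 3-month point.

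Three other outcomes are collected by staff in the room:
- Adjuncts (IX.b.ii): "Data will be collected by study staff observing the procedure", with the medical record as a second source.
- Procedure length (IX.b.iii): "This secondary outcome, measured in minutes, will be collected by study staff observing the procedure".
- Personnel needed (IX.b.vi): also from staff observation.

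The adjunct outcome is defined by use: "This secondary outcome examines the need for adjuncts to control pain/anxiety including LET, injected lidocaine, anxiolytics or systemic pain medications, ketamine sedation or others". Section VII leaves that use open: "Additional topical or injected anesthetics or the use of sedation will be left up to the patient/parent and provider's discretion".

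Sections XI and XVIII separately provide for surveillance of medical risks in each subject, not restricted to wound events. Adverse events and unexpected problems are reported to the IRB (sections XII and XVIII).

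**The concern.** The safety part of the hypothesis is a comparison between arms, so it depends on which events reach that comparison. As written, the outcome depends on what a parent reports three months later. That is a reasonable source for infection or dehiscence. It is a weak one for an event during sedation, a reaction to an injection, or a change of closure method partway through the procedure.

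These events need not be balanced across arms. If sedation is used less in the Dermabond and Steri-Strips arms, as the plan expects, events caused by sedation would tend to fall in the suture arm. A closure that does not hold before the child goes home is a plausible problem in the other two arms. Leaving out the first would flatter sutures, and leaving out the second would flatter the alternatives, so the direction of any error cannot be stated in advance. A child whose assigned closure was replaced before discharge could also be reported at 3 months as free of complications, with nothing in the outcome showing the change.

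**Working it through.** The plan states no figure for complications, so there is none to reproduce. The check is a comparison of the text, followed by arithmetic on scale.

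**Which source is assigned to which event**

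| Event | Where the protocol places it | Compared by arm? |
|---|---|---|
| Infection, dehiscence | IX.b.viii, parent report at 3 months | Yes, as a secondary outcome |
| Use of sedation or anesthetic | IX.b.ii, staff observation and medical record | Yes, as a secondary outcome |
| Adverse event caused by sedation, anesthetic or closure material | Surveillance and IRB reporting (XI, XII, XVIII) | Not stated |
| Closure failed or changed before discharge | Not named in the body text | Not stated |

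The protocol names sources outcome by outcome. Section VII (Data Acquisition) lists chart review as a general source but does not tie it to complications. Section VIII makes the allocated arm the predictor, and section XV does not mention changes of method. Followed exactly, the body text therefore leaves the last two rows out of the arm comparison.

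**Scale**

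Input from section XV: 30 children per arm, 90 in total. Every rate below is an assumption.

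- One event in an arm: 1/30 = 3.3 percentage points.
- Expected events in the ED among 90 children at assumed rates of 1%, 2%, 5% and 10%: 90 × rate = 0.9, 1.8, 4.5 and 9.
- Chance of at least one such event, 1 − (1 − rate)^90: 0.60, 0.84, 0.99 and above 0.999.
- Sedation events in the suture arm, if 20% to 40% are sedated and 5% to 20% of those have an event: 30 × 0.20 × 0.05 = 0.3, up to 30 × 0.40 × 0.20 = 2.4.
- Changes of method, if 5% to 15% of each non-suture arm: 30 × 0.05 = 1.5 to 30 × 0.15 = 4.5 per arm, or 3 to 9 over the two arms.
- One-sided 95% upper bound when no event is recorded, 1 − 0.05^(1/n): 9.5% for n = 30 and 3.3% for n = 90. The bound covers only the kinds of event that were actually ascertained.

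**The case against.** A reader might infer that harms in the ED are never counted. The documents do not support that. Surveillance under sections XI and XVIII covers each subject and extends beyond wound events, and sections XII and XVIII send events to the IRB. A serious sedation event should therefore be known to the investigators. What the protocol does not say is that such an event enters the complications outcome or any table by arm. Section XII is also confined to unexpected problems, and a closure that is simply redone may not count as an adverse event at all.

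Further points against the concern:

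- **The event list is open-ended.** This stands, so it cannot be said that only wound events qualify. But an open list widens the events, not the source or the time point.
- **The forms are missing.** The Subject Data Form, treatment arm protocols and questionnaires (Appendices III, IV and VI) are not in the text reviewed. They may already record the method used or an event in the ED. The point is confined to the outcome definition in the body text.
- **Injected anesthetic.** A reader might infer that the plan expects more injected lidocaine with sutures. It predicts less need for sedation in the other arms and makes no prediction by arm for lidocaine.
- **The rates are assumed.** This stands. Eligibility is limited to small, simple, linear wounds not needing deep sutures, and nothing in the documents supports any particular rate of conversion.
- **A conversion may be a deviation, not a complication.** This is fair. It is a reason to report conversions visibly and separately, not to leave them unrecorded. Their handling in the cosmetic analysis is a different question.
- **The trial is too small to settle safety.** This also stands: zero events in 30 still allows a true rate of up to 9.5%. Better ascertainment makes the description more complete; it does not make the trial able to show that risk is not increased.

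**Conclusion.** The point holds as a gap in the outcome definition. Complications are taken from parent report at 3 months. The body text does not bring procedural events, failed or changed closures before discharge, or surveillance findings into a comparison by arm, although staff are present to record them. The comparison behind the safety part of the hypothesis may therefore miss events that differ between arms, in either direction.

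The size cannot be derived from the documents. The counts above show only that a handful of events is possible and that each moves an arm by 3.3 points. The conclusion assumes that the appendix forms do not already supply these data to the outcome. If they do, section IX.b.viii needs only to say so. Sample size is unaffected. The change is worth making because it is cheap and the visit is a better source for these events than recall three months later.

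**What to change.** Amend section IX.b.viii so that:

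1. Adverse events of sedation, anesthetic or closure material, and any closure failure or change of method before discharge, are recorded at the visit by the staff already observing and checked against the medical record.
2. The 3-month wound events are kept as planned, with the in-person return named as the alternative source.
3. Events found by the surveillance in sections XI and XVIII feed the same table.

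Report items 1 and 2 as separate rows by assigned arm, with a child whose method was changed kept in the assigned arm. Base the statement on complications on both rows, with exact confidence intervals given the small numbers.

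The cost is a few fields on a visit form (fewer if the existing forms already hold them) and one extra table row per arm. It adds no visits or subjects and does not change care. The one downside is that an arm may show more events than under the current definition. Events recorded at the visit also do not depend on reaching the family at 3 months.
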